4.0 Study Procedures

4.1 Primary Study Procedures: The study involves 4 sessions: Informed Consent, Fallypride PET + placebo, Fallypride PET + oral d-amphetamine, and PE2I PET. The 3 PET sessions will be conducted within a 6 week window, and whenever possible within a 2 week time period.

4.2. Informed consent session: Informed consent will be obtained by [name] or approved study personnel after inclusion and exclusion criteria have been reviewed. This will be done in the Dept. of Psychology at Vanderbilt University. Written consent materials are provided to the participant originally when they complete the related IRB protocol #141812. Although given to participants during Part I of the study, Participants only sign the consent for the 2nd part of the study after completing the prior study and passing inclusion and exclusion criteria assessed during that study.

In the present study, participants are given time to read (or reread) the written informed consent document in a quiet private room. They are asked if they have any questions about the protocol. If they have no questions or the researcher has any concerns about whether they understand the procedures, the researcher will briefly review the steps of the study. Because the participants will have already completed IRB #141812, the researchers will already have some knowledge of the participants level of cognitive functioning, and if there is a concern about the participants ability to understand the procedures based on their past performance on cognitive measures they will be excluded from the study.

After the potential participant indicates they have read the document, [name] or his associate will briefly review specific procedures and their risks (especially those related to administration of amphetamine and PET radioisotopes), and the subject will be given a chance to ask questions. The participants will only be asked to sign the informed consent document after any and all questions have been answered.

After signing the informed consent, participants will receive a brief training on how to perform the two-stage task (this will help reduce the amount of time needed for training on that task on the fallypride PET scan days). Participants will also complete the Tests of Vigilance and Attention (TOVA: <http://www.tovatest.com/>), which assesses attention abilities and motor impulsivity.

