5.0 Risks

Possible risks from the study include administration of radiopharmaceuticals and oral d-amphetamine, venipuncture, and the discomforts associated with PET scanning

Radiopharmaceuticals: Subjects are exposed to radiation from the two [¹⁸F]fallypride scans and, the single [¹⁸F]FE-PE2I scan, and the CT scans that are used for attenuation correction. The total radiation dose associated with one PET study is approximately 1900 mrem. This dose corresponds to the background radiation received in 6 years from the environment. Dosing at this level is within FDA guidelines, and large-scale studies of the long-term risk of radiation exposure (within FDA limits) have shown no increase in rates of cancer associated with this amount of exposure.

In addition, there is a potential adverse response to the injections themselves. This risk is minimal because [¹⁸F]fallypride and [¹⁸F]FE-PE2I are injected at subpharmaceutical (tracer-level) doses, and procedures are in place to ensure quality control in terms of requirements for high specific activity, chemical purity and demonstrated sterility. [name] and colleagues have now performed over 200 [¹⁸F]fallypride PET studies at Vanderbilt and have seen no laboratory abnormalities from administration of this radiopharmaceutical. The only adverse event seen in these studies was a single subject who became nauseous, but review of the case suggested that this may have related from hypoglycemia due to fasting before the study.

We lack past experience with injecting [¹⁸F]FE-PE2I at Vanderbilt, but no reports of adverse events have been reported at other institutions using the radioligand, and qualifying runs have shown suitable specific activity, chemical purity and sterility. A nuclear medicine physician will be available within the Department of Radiology in case a problem arises that requires attention.

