7.0 Statistical Analysis Plan

Aim 1 tests the hypothesis that aspects of mesolimbic DA function are associated with age differences in decision behavior.

PET Analyses. A region of interest (ROI) approach will be used in the first set of analyses to examine age group differences in D2 binding (placebo BP_{ND}), DA release (Δ BP_{ND}), and DAT uptake in a set of eight brain areas. We will define subcortical (e.g., caudate, putamen, globus pallidus, thalamus) ROIs based on adapted methods developed for adults of various ages [173] by consultant [name]. We will define a lateral cortical ROI based on the results of a PCA (as in [153]) We will also anatomically define smaller key regions of interest in the midbrain (VTA/SN), ventral striatum (nucleus accumbens), and ventromedial prefrontal cortex using previously published guidelines [110,111] within individual subjects. For initial analyses all ROIs

will be averaged bilaterally, but follow-up tests will also be conducted to determine whether any ROIs warrant bilateral specification. D2 BP_{ND} (placebo) will be extracted for all eight ROIs, while DA release (Δ BP_{ND}) and DAT expression will be extracted from ROIs restricted to only those where there is substantial signal to noise (e.g., VTA/SN and striatal sites for DAT).

We will first test for expected age related differences in DA variables, using ANOVAs with Age group as the independent between subjects variable of interest. Separate analyses will be performed for BP_{ND}, Δ BP_{ND}, and DAT measures. We will also test for interactions between age group and region to test the hypothesis that there will be larger age differences in DA D2-like receptor availability in the pallidum and frontal cortical regions, but smaller (but measurable) declines in the ventral striatum. We expect that middle-aged adults will show significantly lower levels of DA release in the striatum and medial prefrontal cortex and DAT expression in the striatum compared to younger adults.

We will next test whether the dopaminergic measures predict behavioral differences in decision making. Across both groups, we expect individuals with greater DA release in the ventral striatum and ventromedial prefrontal cortex to be more tolerant of effort costs.

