Relative Influence of Different DA Measures. By assessing multiple aspects of the DA system it will be possible to assess the relative influence of different aspects of the DA system on behavioral measures. We will first use a PCA analysis of ROI data for cortical and subcortical ROIs for binding potential, striatal and ventromedial prefrontal DA release, and striatal and midbrain DAT. We expect there to be a positive correlation between all of these variables, reflecting an overall integrity of the DA system, but for separate components to arise reflecting region and measure specific variance [153]. We will then assess the relative impact of the DA variables, by utilizing step-wise regression to determine which variables provide the strongest influence on the behavioral variable, and whether, as predicted, a combination of DA measures provides significantly greater explanation of the behavioral variable than the measures taken in isolation. Further, we expect the inclusion of each additional measure of DA function to reduce the significance of the age effect on differences in sensitivity to effort costs. We expect that a model that includes D2 receptors, DA release, and DAT expression will reduce the age effect to

non-significance, indicating that the age effects are mediated by the DA variables. We will also formally test a mediation model.

Control for Morphometry: When imaging the aging brain it is extremely important to address age differences in morphometry. Aside from common issues that arise with BOLD fMRI [108], findings from prior PET studies of aging may be limited by a lack of control for morphometric changes with age. Lacking information on morphometry, it is possible that observed declines in striatal D2 BP_{ND} could be partially due to changes in grey matter rather than a specific D2 deficit. An additional *innovation* of this project is that we will examine the role of morphometric change, by directly examining whether controlling for grey matter volume changes the results, applying partial volume averaging corrections for ROI analyses, and voxelwise procedures based on voxelwise morphometry techniques (see [154,174] for method details and feasibility).

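### Ranking D2, DA release and DAT by step-wise regression tends to understate whichever is measured least reliably (likely release relative to D2, possibly DAT), by an amount the documents do not let us fix

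*Combined protocol and SAP*

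**What the plan says.** Section 7.0 analyses "D2 binding (placebo BP_{ND}), DA release (Δ BP_{ND}), and DAT uptake in a set of eight brain areas". Section 4.1 lists the sessions that supply them: "Fallypride PET + placebo, Fallypride PET + oral d-amphetamine, and PE2I PET". D2 is therefore the placebo fallypride scan, and release is the change between that scan and the d-amphetamine scan. DAT comes from what Section 5.0 calls "the single [¹⁸F]FE-PE2I scan".

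Under Relative Influence of Different DA Measures, the plan states that "it will be possible to assess the relative influence of different aspects of the DA system on behavioral measures". A PCA of the regional data comes first. The comparison is then made by "utilizing step-wise regression to determine which variables provide the strongest influence on the behavioral variable". The same paragraph asks whether a combination of measures explains more than single measures, and whether adding DA measures removes the age effect.

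On measurement noise there is one provision, under PET Analyses: release and DAT "will be extracted from ROIs restricted to only those where there is substantial signal to noise". No test-retest reliability is given for any measure. No correction for measurement error is described, and there is no caution about comparing measures of unequal precision.

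**The concern.** A regression on observed values cannot separate a weak influence from a poorly measured one. Error in a predictor shrinks its coefficient, delays its entry in a step-wise procedure and passes part of its effect to correlated competitors. The plan expects such correlation: "We expect there to be a positive correlation between all of these variables".

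Release carries the error of two scans, over a true between-person spread that is only that of the displacement. D2 carries the error of one scan. That scan also enters release, so the errors of D2 and release are correlated as well. DAT uses a different tracer with no reliability figure; Section 5.0 says the site had not injected it before.

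At stake is the answer to the question this analysis poses. A report that receptor or transporter levels matter more than release could reflect only that they were measured better. The same applies to release as a mediator of the age effect. Replacing step-wise selection with a pre-specified joint model would remove the selection problem but not the attenuation.

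**Working it through.** **Inputs from the documents.** The definitions of the three measures and the scans behind them (Sections 4.1, 5.0, 7.0); 60 completers, 30 per age group (Section 3.2); positive correlation among measures, size not given.

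**Assumptions.** Single-scan reliability R, true spread of release, correlation among the true measures, and equal true standardised effects of .30. The documents give none of these, so ranges are shown.

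**Step 1. The nearest stated figure.** The plan gives no figure for the ranking. Its sample size for r = .5 with two covariates is n = ((1.960 + 0.842)/atanh(.5))² + 3 + 2, just over 31, which rounds up to the stated 32. It reproduces. Its r = .5 rests on past correlations with BP_ND, not with change in BP_ND.

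**Step 2. Reliability of a two-scan difference.** With s the true SD of fractional release and e the scan error, reliability is s²/(s² + 2e²).
- s = 8%, e = 3%: 64/(64 + 18) = .78
- s = 6%, e = 5%: 36/(36 + 50) = .42
- s = 10%, e = 3%: 100/(100 + 18) = .85

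Relative to D2, let k be the true SD of release divided by the true SD of D2. Reliability of release is then k²/(k² + 2(1−R)/R). At R = .90 this gives .82, .69, .53 and .29 for k = 1, 0.7, 0.5 and 0.3. Write v = (1−R)/R. Release is less reliable than D2 when k²/(k² + 2v) < 1/(1 + v), which reduces to k² < 2. So, with equal error on each scan, release is the less reliable unless its true spread exceeds about 1.4 times that of D2.

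**Step 3. Effect on the ranking, independent errors.** Simulation, n = 60, 20,000 runs, true correlations .3, D2 and DAT reliability .9. First means the largest correlation with behaviour; last means the weakest in the joint model.

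| Release reliability | Release first | Release last | Release coefficient | D2 and DAT coefficients |
|---|---|---|---|---|
| .9 | 33% | chance (33%) | equal | equal |
| .78 | 25% | 41% | – | – |
| .7 | 20% | 47% | .25 | .31 |
| .5 | 10% | 61% | .21 | .32–.33 |
| .4 | 6% | 69% | .18 | .33 |

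If release truly has twice the influence of the others (.4 against .2), it ranks first in 73–74% of runs at reliability .9 but in 36% at .5.

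**Step 4. Adding the shared placebo scan.** Simulation with forward entry, 8,000 runs per setting, R = .90, correlation .3.

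| k | Release enters last | Mean coefficients D2 / release / DAT |
|---|---|---|
| 1.0 | 44% | .28 / .25 / .31 |
| 0.7 | 55% | .29 / .22 / .32 |
| 0.5 | 68% | .30 / .17 / .34 |

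At k = 0.5 with independent errors, release enters last in 59% and its coefficient is .22. Sharing the scan therefore lowers the release coefficient from .22 to .17. Over 36 settings (R of .80, .90, .95; k of 0.3 to 1.0; correlation 0, .3, .5; DAT as reliable as D2), release enters last in 38% to 91%, and in more than half of runs in 24 of the 36.

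**Step 5. Letting DAT be noisier.** With independent errors, D2 at .9 and release at .7, DAT at .7 puts release and DAT last about equally often (roughly 40% each). With DAT at .6, DAT is last in 46% and release in 35%. With shared error, R = .90 for D2, k = 1 and DAT at .5, release is last in 30%, slightly below chance.

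**Step 6. The separate test of release.** If r = .5 is what a single scan with R = .90 shows, the matching r for release is .5 × √(reliability/.90), which is .48, .38 or .28 at k = 1, 0.5 or 0.3. Power at N = 60 with three covariates is then .97, .84 or .57.

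**Limits.** The documents do not say whether change is absolute or percent, or whether PCA components or regional values enter the regression. Pooling regions could raise reliability. Neither this nor an age term was modelled.

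**The case against.** A reader might infer that release will usually come out weakest. The documents do not support that. At release reliability .7 to .78 it is last in fewer than half of runs, and at k = 1 with R of .90 or more in 38–44%. Whether it passes one half depends on scan reliability and on the spread of true release, and neither is given.

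A reader might also infer that DAT is as precise as D2 because each is a single scan. That does not follow for a different tracer, and Step 5 shows that DAT can be the understated measure.

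Three further objections have weight.
- The plan is not silent on noise: the signal-to-noise restriction is a real, if partial, step. It screens regions; it does not make the three measures equally reliable.
- The PCA may reduce noise. It may, but nothing in it equalises reliability across measures.
- Aim 1's prediction about release and effort tolerance is tested separately, before any ranking. This stands. Attenuation there costs power; it does not reverse the conclusion. Whether a combination of measures does better than single ones also needs no ranking.

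On the remedy, a correction using reliabilities alone assumes independent errors, which fails for D2 and release. That objection is right, and the fix below allows for it. So is the warning that at n = 60 a corrected ranking will often be inconclusive.

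**Conclusion.** The concern holds as a directional bias of unknown size. Using step-wise results to name the most influential DA measure tends to understate the least reliable one. That is likely release relative to D2, given the two-scan difference and unless release varies much more between people than D2 does. It may also be DAT.

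Under equal true effects, n = 60 and D2 and DAT reliability of .9, release ranks first about 25%, 20% and 10% of the time at reliability .78, .7 and .5, against 33% by chance. The shared placebo scan lowers its coefficient further. These figures rest on assumed reliabilities, correlations and effects, and show scale only.

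The point concerns a secondary comparison and its use in interpreting mediation. It does not undermine the separate Aim 1 test.

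**What to change.** In Section 7.0, Relative Influence of Different DA Measures:

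- Do not infer relative influence from step-wise entry order or p-values.
- Report standardised D2, release and DAT coefficients from one pre-specified model with age group. State which regions or PCA components enter. Give 95% confidence intervals for the coefficients and for their pairwise differences.
- Add a sensitivity analysis with measurement-error correction over a stated reliability range for each measure, for example release .4 to .9, D2 .8 to .95, and a wider range for DAT extending below .8. Model the correlated D2–release error from the shared placebo scan.
- If the sign of a difference is not stable across plausible reliabilities, state that relative influence is unresolved. Give the same caveat for release as a mediator.

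The cost is SAP wording and one sensitivity analysis, with no new data. The downside is wider intervals: in simulation with release reliability .5, the corrected release coefficient had an SD of about .20 around a true value of .30. A ranking will often not be possible.

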 - k) Diabetes, hypoglycemia, or any condition that could would prevent the participant from fasting for 6 hours
 - l) Recent participation in studies involving radiation or routine occupational exposure to radiation.
 - m) High blood pressure (Systolic B.P. > 150), or an abnormal EKG indicating potential cardiac risk under conditions of increased blood pressure. If subject is over 60, baseline B.P. > 145.

Inclusion/Exclusion criteria are determined based on data obtained during IRB#141812 (with the exception of the plasma pregnancy exam for women of child-bearing potential which is collected within 48 hours prior to each PET scan. At any point in the study, the study PI ([name]), or one of the study physicians may withdraw a participant if they find new evidence that the participant has an exclusionary condition.

Up to 70 subjects may be consented for the study, with the aim of having 60 subjects total complete the PET studies. No more than 60 subjects (30 per age group, with equal gender representation). No subjects will be consented after the 60th participant is scheduled for a PET scan unless we have another withdrawal from the study.

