Statistical Power: The analyses of age differences will be conducted with age as a dichotomous variable. The group difference effects that have been observed in relevant recent studies of decision making or corticostriatal brain activity [109-112] range from around $d=0.75-1.5$. To detect the lower extent of these effects, a total sample size of at least 60 (30 per group) is recommended for a power of .80 at $p < .05$ two-tailed. Across the sample and within age groups, we will examine relationships between continuous measures (e.g., task performance, cognitive ability, emotional traits, fMRI neural activity, PET DA measures). The individual difference correlations that have been observed in related studies range on average from $r=0.3-0.6$. To detect an average correlation of $r=.5$ within each age group (with up to two other covariates in the model), a sample size of at least 32 is recommended for a power of .80 at $p < .05$ two-tailed. Individual difference analyses that combine the age groups ($N=64$) will provide a power of over .95 to detect a correlation of $r = .50$ at $p < .05$ two-tailed (allowing for up to three covariates in the model). An r of this level is consistent with our past level of correlations between individual difference measures and DA BP_{ND} within healthy young samples [78,79]. We will also require this sample size to have sufficient power to detect interaction effects (see later hypotheses on age differences in DA measures).

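### Correlation power is stated for 32 per age group and 64 in total, but the planned PET sample is 30 per group and 60 in total

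*Combined protocol and SAP*

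**What the plan says.** The Statistical Power paragraph of section 7.0 uses two different sample sizes.

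- **Age-group difference:** 60 in total, 30 per group, for d = 0.75 at power .80.
- **Correlation of .5 within an age group, up to two covariates:** "a sample size of at least 32 is recommended for a power of .80", at two-sided .05.
- **Correlation of .50 across both groups, up to three covariates:** "Individual difference analyses that combine the age groups ($N=64$) will provide a power of over .95".

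The variables listed for the correlation analyses include "emotional traits, fMRI neural activity, PET DA measures". The choice of .50 is supported by earlier correlations with dopamine binding potential, which is a PET measure. The paragraph ends: "We will also require this sample size to have sufficient power to detect interaction effects".

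Section 3.2 sets the sample: "Up to 70 subjects may be consented for the study, with the aim of having 60 subjects total complete the PET studies". It continues "No more than 60 subjects (30 per age group, with equal gender representation", and then: "No subjects will be consented after the 60th participant is scheduled for a PET scan unless we have another withdrawal from the study".

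**The concern.** A power statement should describe the sample that the study plans to have. Here the plan recommends at least 32 per age group for the within-group correlations and then plans 30. No section plans 32 per group or 64 PET completers, and the 70 in section 3.2 is a ceiling on consents, not a target for completers.

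Correlations with PET measures carry much of the analysis. Aim 1 relates dopamine release to effort tolerance. Aim 3 relates the drug's effect on effort to transporter function and dopamine release. A reader would take the stated power to apply to these analyses.

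The closing sentence comes straight after the one on 64, so it reads as requiring 64 for interaction effects. Interaction power is given at neither 60 nor 64.

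**Working it through.** **Inputs.** From section 7.0: two-sided alpha .05; r = .5; k = 2 covariates within a group and k = 3 pooled; stated sizes 32 and 64; d = 0.75 for the age-group difference. From section 3.2: 30 per group, 60 in total.

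**Methods.**
- Fisher z: power ≈ Φ(atanh(r)·√(n − 3 − k) − 1.960), with atanh(.5) = 0.5493. The opposite tail is negligible.
- Exact (bivariate normal, random predictor): t test of the partial correlation on n − k − 2 degrees of freedom. Power is the noncentral t probability with noncentrality [r/√(1 − r²)]·√U, averaged over U, a chi-square with n − k − 1 degrees of freedom.

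**Step 1: reproduce the plan's figures (Fisher z).**
- n = 32, k = 2: 0.5493·√27 − 1.960 = 0.894, power 0.814.
- n = 31, k = 2: 0.5493·√26 − 1.960 = 0.841, power 0.7998, just short of .80.
- So 32 is the smallest n that reaches .80 by this method, which matches the plan. By the exact method the smallest n is 31.
- N = 64, k = 3: 0.5493·√58 − 1.960 = 2.223, power 0.987, so the claim of more than .95 is correct.

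**Step 2: repeat at the planned PET sample.**
- n = 30, k = 2: 0.5493·√25 − 1.960 = 0.787, power 0.784.
- N = 60, k = 3: 0.5493·√54 − 1.960 = 2.077, power 0.981.

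| Analysis, r = .5 | n | Covariates | Fisher z | Exact |
|---|---|---|---|---|
| Within group, as stated | 32 | 2 | 0.814 | 0.828 |
| Within group, as planned | 30 | 2 | 0.784 | 0.799 |
| Within group, as planned | 30 | 1 | 0.800 | 0.814 |
| Within group, as planned | 30 | 0 | 0.814 | 0.828 |
| Pooled, as stated | 64 | 3 | 0.987 | 0.988 |
| Pooled, as planned | 60 | 3 | 0.981 | 0.982 |

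A simulation of 400,000 runs with two covariates gave 0.798 at n = 30 and 0.827 at n = 32, in agreement with the exact column.

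**Step 3: related quantities.**
- Smallest correlation detectable at 80% power with two covariates: 0.508 (Fisher z) or 0.500 (exact) at n = 30, and 0.492 or 0.485 at n = 32.
- Pooled N needed for power .95 with three covariates: 50 (Fisher z) or 49 (exact), well below 60.
- Age-group difference, two-sample t test, d = 0.75, 30 per group: power 0.815; 29 per group already reaches .80.

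Interaction power was not computed, because the plan gives no interaction effect size.

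**The case against.** The strongest reply is that no calculation in the paragraph is wrong and that almost nothing depends on the difference. Two of the three power claims hold unchanged at 60. The third slips only with the full two covariates, and by less than the choice of method matters: a fixed-predictor F test gives 0.861 at n = 30. This is correct about size, and it makes the point an inconsistency between sections, not a miscalculation. The F-test figure does not rescue the text, however. That method does not reproduce the plan's 32, and it treats as fixed a predictor that is measured.

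The second reply is that 32 and 64 may describe analyses without PET. Task and fMRI data come from Part I, whose sample size is not given here. Up to 70 people may be consented, and an attention test is done at the consent session. So 64 is possible for some measures, but the document does not say so, and the paragraph names PET measures and justifies its r from them. A subject who withdraws and is replaced might also still supply one PET measure, so 60 is the planned size and not a strict ceiling for every measure.

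The third reply is that the missing interaction power is a separate matter, and that the closing sentence could mean either total. That is fair. The core point does not depend on it, but the wording needs settling in the same edit.

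**Conclusion.** The point holds as a minor inconsistency. The stated sizes of 32 and 64 are not the PET sample planned in section 3.2. At the planned size, within-group power for r = .5 with two covariates falls from 0.814 to 0.784 by Fisher z, the method that reproduces the plan's 32, or from 0.828 to 0.799 by the exact method. With one covariate or none it is about .80 or higher. The pooled and age-group claims remain true at 60. No aim or test has to change.

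These figures assume that all 30 per group supply the PET measure in question, that the variables are jointly normal, and that the plan's own r = .5 applies. Confidence in the mismatch is high. Where 64 came from cannot be determined from the document.

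**What to change.** Restate the two correlation sentences at the planned PET size. For example: with 30 per age group, power to detect r = .5 within a group (two-sided .05) is about .78 by Fisher z, or .80 by the exact method, with two covariates, and about .80 or more with one or none; with both groups combined (N = 60), power to detect r = .50 is about .98 with up to three covariates. If 32 and 64 are meant only for analyses that need no PET measure, say which analyses those are.

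Reword the closing sentence so that it does not point to 64. Either give a computed interaction power at 60 with its assumed effect size, or state that interaction power was not computed. Without that computation, do not claim that 60 is sufficient for interactions.

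The cost is a text edit, with no extra participants or procedures. The stated within-group power becomes at most slightly less favourable.
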